### 5.3.2. Covariates

The list of demographic and clinical characteristics considered for descriptive reporting, subgroups and inclusion as covariates in models for generating the propensity scores are provided in Table 5.3. The Komodo Health database will be source of all variables.

Patients will be considered to have a comorbidity or hospitalization during baseline if there was evidence of a diagnosis at any time during the baseline period. Evidence of comorbidities or hospitalization during follow-up will be considered as new diagnoses. Once diagnosed, patients will be considered diagnosed for the remainder of their follow-up. ART adherence during baseline and follow-up will be updated every 6 months (180 days) based on the data collected in that previous timeframe. For baseline annual physical exam and annual influenza vaccine, patients will be considered adherent (coded as 'Yes') if there was evidence of these events at any time during the baseline period. During the follow-up, patients will be considered adherent up to 365 days after the last event date.

For annual CD4 and viral load laboratory tests during baseline and follow-up, patients will be coded as 'Yes' up to 365 days after the last event date. For respiratory virus season during follow-up, patients will be coded as 'Yes' if the observation time is in October, November, December, January, February, March or April.

The baseline period for the assessment of covariates is the six months prior to the index date, i.e., no data prior to six months will be included.

Covariates used at baseline only will be considered time-fixed confounders. Covariates additionally or only used during follow-up will be considered time-varying confounders.

Categories may be collapsed, or covariates may be excluded from the propensity scores if models fail to converge.

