#### **5.8.4. Inverse Probability of Treatment Weighting for Time-Varying Exposures**

Except for patients vaccinated more than 13 days before the end of the baseline period, exposure (vaccination) status will not be fixed at start of follow-up, with patients able to receive PCV13 during follow-up. Therefore, PCV13 will be considered a time-varying exposure. The values for some clinical characteristics may also change during the study period and values during baseline may be poor proxies for covariate values at the various points during the follow-up. Therefore, some covariates will be treated as time-varying confounders (Section 5.3.2).

Inverse probability of treatment weighting (IPTW) will be generated from predicted probabilities of vaccination status (propensity scores) to create pseudo-populations where any imbalances in the potential confounders by vaccination status are reduced. For the analyses of first events, stabilized weights will be generated for each patient for the baseline period and every 30 days from index during the follow-up until the earliest of the following: outcome, death, end of health plan enrollment or end of study period. For the analyses of recurrent events, stabilized weights will be generated for each patient for the baseline period and every 30 days from index during the follow-up until the earliest of the following: death, end of health plan enrollment or end of study period. This aims to make vaccination status independent of the measured confounders at each of the follow-up timepoints [9]. The weights will be used to estimate the average treatment effect (ATE). For the analysis of RZV, stabilized weights will be generated every 90 days instead of 30, due to the expected lower numbers of patients vaccinated with RZV overall and in each interval.

The numerators for the stabilized weights will be the estimated probability of a patient's observed vaccination status at timepoint given their prior vaccination status and time-fixed covariates. The denominators will be the estimated probability of a patient's observed vaccination status at the given timepoint given their prior vaccination status, time-fixed covariates and time-varying covariates. Numerators and denominators after vaccination will be set to 1 and the cumulative product of these ratios will be calculated, therefore IPT

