weights after vaccination will be constant. Time-varying covariates will be lagged, i.e., within each 30-day (or 90-day for RZV) interval the vaccination status will be the status at the end of the interval, whereas the values for the covariates will be from the end of the previous interval. Cox proportional hazards models will be used to model the associations between vaccination status and the numerators and denominators.

It is possible that censoring may be informative, with patient characteristics associated with loss to follow-up. Therefore, patients who are censored may have different risks of the study outcomes than patients who are not censored. Inverse probability of censoring weighting (IPCW) will also be generated during the follow-up using the above methods for IPTW. These weights will be multiplied by the IPT weights to produce a new set of weights [9].

Distributions of the IPT, IPC and IPT\*IPC weights will be summarized by vaccination status. In the presence of extreme/outlier weights, stabilized weights may be truncated at the 1st and 99th percentiles for use in the Cox models for the outcomes. Although there is no formal definition of an extreme weight, the need for truncation will be judged based on the distributions and the potential effect on the interpretation of results [9].

Weights for first and recurrent events will be generated separately in datasets created for each study outcome; however, all weights will be derived without assessing their impact on the VE estimates. Weights will also be generated again in each of the subgroups. The weights will be generated using the *ipwtn* function within the *ipw* R package [10]. Example R code is provided in Appendix 7.2.

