#### **5.8.7. Vaccine Effectiveness**

Crude PCV13 VE percentages will be estimated based on  $(1-HR) \times 100$ , where HR is obtained from unadjusted Cox models for first episodes for each outcome. VE percentages will also be obtained from marginal structural Cox models (Cox-MSM) after applying the IPT and the IPT\*IPC weights. As the numerators for the stabilized weights will include the index-fixed covariates, those covariates will also be included in the Cox-MSM for the outcomes [9]. Cluster robust standard errors will be used to account for the multiple records per patient. The proportional hazards assumption will be assessed graphically with the inspection of Schoenfeld residuals.

To explore potential changes in VE over time, HRs may also be generated during specific time periods using piecewise Cox models. The time periods will be 0-3 years (0 to 1079 days), 3-5 years (1080 to 1799 days), 5-7 years (1800 to 2549 days).

VE may also be assessed for recurrent events using the Andersen-Gill (AG) model [11]. For each outcome, subsequent events will be of the same type, e.g., in the analysis of IPD it will be assumed that a patient is only at risk for future IPD events. The VE is assumed constant across the recurrent events.

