### 7.2. Appendix B: R Example Code

#### 7.2.1. Example Data Formats for First Event and Recurrent Events

Example dataset for time to first outcome:

ptid	tstart	tstop	pcv13	ipd	x1	x2	xt1	xt2	censor	endfu
1001	-1	0	0	0	1	0	0	0	0	87
1001	0	30	0	0	1	0	0	0	0	87
1001	30	60	1	0	1	0	1	0	0	87
1001	60	87	1	0	1	0	1	0	1	87
1002	-1	0	0	0	0	0	0	0	0	45
1002	0	30	0	0	0	0	0	1	0	45
1002	30	45	0	1	0	0	1	1	0	45

Example dataset including any subsequent outcomes:

ptid	tstart	tstop	pcv13	ipd	x1	x2	xt1	xt2	censor	endfu2
1001	-1	0	0	0	1	0	0	0	0	87
1001	0	30	0	0	1	0	0	0	0	87
1001	30	60	1	0	1	0	1	0	0	87
1001	60	87	1	0	1	0	1	0	1	87
1002	-1	0	0	0	0	0	0	0	0	106
1002	0	30	0	0	0	0	0	1	0	106
1002	30	45	0	1	0	0	1	1	0	106
1002	45	60	0	0	0	0	1	1	0	106
1002	60	84	0	1	0	0	1	1	0	106
1002	84	90	0	0	0	0	1	1	0	106
1002	90	106	0	0	0	0	1	1	0	106

Where:

- *ptid*: patient identifier
- *tstart*: first day of interval. -1 represents baseline period
- *tstop*: last day of interval
- *pcv13*: binary indicator for time-varying PCV13 vaccination status (exposure)
- *ipd*: binary indicator for IPD event (outcome)
- *x1, x2, ..., xn*: time-fixed confounders
- *xt1, xt2, ..., xtn*: time-varying confounders
- *censor*: binary indicator for censoring event

- *endfu*: last day of follow-up up to any first event
- *endfu2*: last day of follow-up

For binary variables, 1 indicates Yes, 0 indicates No. Note, all variables in dataset must be numeric for the *ipwtn* function.

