### 7.2.2. Code for Generating IPTW and IPCW

```
library(ipw)
iptw <- ipwtn(exposure = pcv13, family = "survival",
numerator = ~ x1 + x2 + ... + xn, denominator = ~ x1 + x2 + ... + xn + xt1 + xt2 + ... + xtn,
id = ptid, tstart = tstart, timevar = tstop, type = "first",
data = ipdfirst)
ipcw <- ipwtn(exposure = censor, family = "survival",
numerator = ~ x1 + x2 + ... + xn, denominator = ~ x1 + x2 + ... + xn + xt1 + xt2 + ... + xtn,
id = patient, tstart = tstart, timevar = tstop, type = "cens",
data = ipdfirst)
iptw.stab<-iptw$ipw.weights
ipcw.stab<-ipcw$ipw.weights
ipdfirst<-cbind(ipdfirst, iptw.stab, ipcw.stab)
ipdfirst$comb.weights<- ipdfirst$iptw.stab*ipdfirst$ipcw.stab

#Plot of stabilized weights during follow-up in unvaccinated
ipwplot(weights = subset(ipdfirst$iptw, ipdfirst$pcv13==0),
subset(timevar = ipdfirst$tstop, ipdfirst$pcv13==0),
binwidth = 183, ylim = c(-1.5, 1.5), main = "Stabilized weights",
xlab = "Years Since Index", ylab = "Logarithm of Stabilized IPTW",
xaxt = "n", yaxt = "n")
axis(side = 1, at = seq(0, 15, 1), labels = as.character(seq(0, 15, 1)*0.5))
axis(side = 2, at = c(-1.5, -1, -0.5, 0, 0.5, 1, 1.5),
labels = as.character(c(-1.5, -1, -0.5, 0, 0.5, 1, 1.5)))
```

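### One Cox weight model spans the baseline row and all follow-up intervals, so if a time-varying covariate affects uptake differently in the two periods, VE can show a false trend across the 0-3, 3-5 and 5-7 year windows

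*SAP*

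**What the plan says.** SAP 5.8.4 plans that "stabilized weights will be generated for each patient for the baseline period and every 30 days from index during the follow-up", and that "Cox proportional hazards models will be used to model the associations between vaccination status and the numerators and denominators".

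The example dataset in SAP 7.2.1 enters the six-month baseline period as one row, with tstart described as "first day of interval. -1 represents baseline period", above the 30-day rows. SAP 7.2.2 fits the whole dataset in one call, beginning "iptw <- ipwtn(exposure = pcv13, family = 'survival". The formulas contain main effects only. The incidence-rate code in 7.2.3 restricts to tstart of 0 or more; the weight code does not.

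The covariates do not carry the same meaning in the two kinds of row:

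- **Lag.** In follow-up, values come from the end of the preceding interval (5.8.4). Baseline values come from the same six months in which baseline doses fall, and nothing earlier is used (5.3.2).
- **Look-back.** Physical exam and influenza vaccine count at baseline "if there was evidence of these events at any time during the baseline period". In follow-up each record counts for 365 days.
- **Season.** Respiratory virus season is a follow-up-only covariate (Table 5.3), so it has no baseline-row value.

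Two checks are planned. SMDs are computed for the baseline period and each interval, and a variable above 0.1 after weighting may be added to the outcome model (5.8.5). For the Cox models, "The proportional hazards assumption will be assessed graphically with the inspection of Schoenfeld residuals" (5.8.7); the code in 7.2.5 applies this to the outcome model.

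**The concern.** A Cox weight model lets the level of uptake differ freely from row to row, but holds each covariate's hazard ratio constant across rows. Here that means one ratio for vaccination by index and for vaccination in any interval over the following years. If the two true ratios differ, the fitted one lies between them. Baseline vaccinees are then mis-weighted in one direction, and later vaccinees in the other.

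Weights are fixed once a person is vaccinated (5.8.4), so an error made in the baseline row persists through every window. Baseline vaccinees supply most of the early vaccinated time and later vaccinees a growing share afterwards, so opposite errors appear as a change in VE with time since index. Every primary and secondary objective asks for VE at 3, 5 and 7 years where feasible, and such an artefact could be read as waning or as lasting protection.

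**Working it through.** **Planned precision, for scale.** No figure in the plan bears directly on this bias; the nearest is Protocol Table 2. For IPD with VE 22.5%, 97 months, 4% censoring and D = 1,452 events, use 1 − HR·exp(±1.96/√(D·p·(1−p))). With HR 0.775 and an assumed time-averaged vaccinated share p = 0.16 (half of 32%), √(1,452 × 0.16 × 0.84) = 13.97 and exp(1.96/13.97) = 1.151. The limits are 10.8% and 32.6%, matching the stated 11 to 33. At 36 months and 4% censoring, the planned half-widths are (19 − 11)/2 = 4 points for all-cause pneumonia at VE 15%, and (37 − 3)/2 = 17 points for IPD at VE 22.5%.

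**Inputs.** From the documents: 32% ever vaccinated, 4% annual censoring, true VE 15% in every window, 30-day intervals and the SAP windows. Assumed: 10% of the cohort vaccinated in the baseline period; one binary time-varying confounder L with prevalence 30%, onset 10% a year and outcome rate ratio 2.5 unless stated; a rare outcome.

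**Model.** The probability of vaccination in row k is 1 − exp(−H_k·g^L), where H_k is free in each row and g is the uptake HR. The stabilized weight is the cumulative product of P(status) over P(status given L). The pooled fit has one g for the baseline row and 85 follow-up rows; the separate fit has one g for each period. VE comes from a weighted, time-stratified hazard model.

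**Baseline row by hand, true g = 2 at baseline and 1 later.**

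1. Solving 0.7(1 − e^−H) + 0.3(1 − e^−2H) = 0.10 gives H ≈ 0.082, so uptake is 7.85% at L = 0 and 15.1% at L = 1.
2. Unweighted, L is present in 0.3 × 0.151/0.100 ≈ 45% of vaccinees and 0.3 × 0.849/0.900 ≈ 28% of the rest (SMD about 0.355).
3. The pooled fit gives g = 1.27, with fitted uptake of about 9.3% and 11.6%.
4. After weighting, L is present in about 40% of vaccinees and 29% of the rest. The SMD is still 0.23.
5. In the first follow-up interval the SMD goes from 0.00 to about −0.11. Weighting creates an imbalance where there was none.

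**VE by window, pooled weights (true value 15.0 throughout).**

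| Uptake HR, baseline then follow-up | Outcome ratio | 0-3 y | 3-5 y | 5-7 y | Change | Max SMD |
|---|---|---|---|---|---|---|
| 2, 2 | 2.5 | 15.0 | 15.0 | 15.0 | 0.0 | 0.00 |
| 2, 1.5 | 2.5 | 13.7 | 15.1 | 15.5 | +1.8 | 0.09 |
| 2, 1 | 2.5 | 11.6 | 15.1 | 16.0 | +4.4 | 0.23 |
| 3, 1.5 | 2.5 | 11.8 | 15.3 | 16.2 | +4.4 | 0.23 |
| 0.5, 1.5 | 2.5 | 19.7 | 15.0 | 13.7 | −6.0 | 0.34 |
| 2, 1 | 1.5 | 13.5 | 15.0 | 15.5 | +2.0 | 0.23 |
| 3, 1 | 4 | 7.2 | 15.4 | 17.3 | +10.1 | 0.37 |

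Separate weight models return 15.0 in every window of every row. Overall VE under pooling is off by at most 1.3 points.

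**Other inputs.** With 20% vaccinated at baseline and uptake HRs 2 then 1, the windows are 12.6, 15.2 and 16.2. A second calculation used true VE 0%, baseline uptake 6 to 15%, prevalence 35%, onset 6% a year, outcome HR 2 to 3 and uptake HR 2 to 3 then 1. It gave −1.5 to −3.1, +0.9 to +2.6 and +1.4 to +4.3: a false rise of 3 to 7 points, with overall VE off by 0.4 to 0.7. The reverse pattern (HR 1 then 2) gave a false fall of 3 to 5.

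**The case against.** **The SAP has a balance check, and acting on it can work.** In the VE 0% calculation with 10% vaccinated at baseline, uptake HRs 2 then 1 and outcome HR 2, adding the covariate's current value to the weighted outcome model brought all three windows back to 0.0. Adding only its baseline value cut the false trend from 4.3 to 1.1 points. This stands, with limits. The SAP makes the step optional. The HR 2 then 1.5 case stays below the 0.1 threshold. The exact correction also needs a covariate that vaccination does not influence; where it does, conditioning on it gives up the reason for using a marginal structural model.

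**Time-fixed covariates are protected.** They are in the numerator, the denominator and the outcome model, and a run with such a covariate gave 0.0 in every window. This stands in full.

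**Different uptake effects are not documented.** The plan gives no uptake hazard ratios. The look-back difference concerns two flags, and CD4 and viral-load testing follow one rule throughout. Just after index, the 365-day flags still draw on the same six months, so the change is gradual. A reader might infer that the pooled weights must fit both periods badly, or that a six-month row beside 30-day rows causes misfit by itself. Neither follows: the free baseline hazard absorbs row length, and with equal effects the pooled model is exact.

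**The windowed results are conditional and imprecise.** They are produced if feasible. Backing log-HR information out of the rounded limits in Protocol Tables 2 and 3, and splitting the post-36-month part equally between two windows, a contrast of 0-3 years with one later window has a half-width of about 5 to 8 VE points for all-cause pneumonia and 27 to 29 for IPD. The bias therefore matters mainly for all-cause pneumonia.

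**The code is labelled an example.** True, but 5.8.4 names the function and refers to that code, and nowhere describes a separate baseline model.

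**Conclusion.** The concern holds conditionally. As written, the SAP forces one coefficient per time-varying covariate across two periods in which its own rules define some of those covariates differently. If the uptake effects differ, a false VE trend can follow, in either direction: about 2 points for a modest difference, which the 0.1 rule can miss, and about 3 to 7 points for larger ones, most of which it would flag. An outcome ratio of 1.5 reduces the larger cases to 2.0 to 3.3 points, and the most extreme inputs reach 10.1.

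These sizes rest on an assumed share vaccinated at baseline, assumed uptake and outcome ratios, and a single confounder; several covariates could add up or cancel. The documents make different effects plausible but do not establish them. Nor do they support a reading that overall VE is seriously compromised, since it moves by about 1 point or less.

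**What to change.** In SAP 5.8.4 and 7.2.2:

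1. Fit a separate model for being vaccinated by index, for example logistic. Put time-fixed covariates in the numerator, and time-fixed covariates plus the baseline values of the time-varying ones in the denominator. Leave season out. Interactions between a baseline-row indicator and the time-varying covariates are an alternative.
2. With the separate model, fit the Cox numerator and denominator models only to rows with tstart of 0 or more, in people unvaccinated at index.
3. Multiply the two weights.

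In SAP 5.8.5, where a post-weighting SMD exceeds 0.1 at baseline or in an interval, respecify the weight model first, for example with a covariate-by-period term. Consider adding the variable to the outcome model only after that. Balance is a better trigger here than a formal proportional-hazards test of the weight model, because with up to 56,000 vaccinations such a test would flag trivial departures.

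The cost is SAP wording, one extra pair of models per dataset and a few more parameters. No new data are needed, and little is lost if the effects prove equal.

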#### **5.8.5. Assessment of Covariate Balance**

Standardized mean differences (SMD) will be calculated for the baseline period and every 30 days (or 90 days for RZV) since index for each of the covariates up to any PCV13 vaccination before and after the IPTW. Overall SMDs will be presented for each covariate before and after the IPTW (such as median and maximum values across the intervals with at least 100 patients vaccinated), as well as those at the end of each year of follow-up (at 360, 720, 1080, 1440, 1800, 2190, 2550, 2910 days). SMDs  $\leq 0.1$  will be considered as evidence of negligible imbalance. Variables with SMDs  $> 0.1$  after IPTW may be added to final weighted outcome models.

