#### 7.2.4. Code for Standardized Differences

```
library(cobalt)
smdDataY1<-subset(ipdfirst[ipdfirst$tstart==360 &
  (ipdfirst$tstart < ipdfirst$pcv13date14 | is.na(ipdfirst$ pcv13date14)),])
#Where pcv13date14 is 14 days after the PCV13 vaccination date
covs <- subset(smdDataY1, select = c(x1, x2, ...))
#Before IPTW
smdsUn<-bal.tab(covs, treat = smdDataY1$pcv13, continuous = "std",
  binary = "std", s.d.denom = "pooled")
x1SmdUn<-smdsUn$Balance[1,2]
x2SmdUn<-smdsUn$Balance[2,2]
...
#After IPTW
smdsWt<-bal.tab(covs, treat = smdDataY1$pcv13, continuous = "std",
```

```
binary = "std", s.d.denom = "pooled", weights=smdDataY1$iptw.stab)
x1SmdWt<-smdsWt$Balance[1,3]
x2SmdWt<-smdsWt$Balance[2,3]
```

```
...
```

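### The 0.1 limit on SMDs in SAP 5.8.5 does not fit the weights it checks: time-fixed covariates keep their imbalance by construction, and a maximum over small intervals usually exceeds 0.1 by chance

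*SAP*

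**What the plan says.** SAP 5.8.5 computes SMDs for each covariate at baseline and every 30 days, among patients not yet vaccinated, before and after IPTW. An SMD of 0.1 or less counts as "evidence of negligible imbalance". Overall SMDs are summarised by statistics "such as median and maximum values across the intervals with at least 100 patients vaccinated", and yearly values are shown "at 360, 720, 1080, 1440, 1800, 2190, 2550, 2910 days". Variables above 0.1 after weighting "may be added to final weighted outcome models".

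The weights come from SAP 5.8.4. The numerator is the probability of the observed vaccination status "given their prior vaccination status and time-fixed covariates"; the denominator adds the time-varying covariates. The code in 7.2.2 does the same. SAP 5.8.4 also states the aim of making vaccination independent of the measured confounders at each follow-up timepoint.

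The example code in 7.2.4 passes the stabilized weights to the SMD function and picks its covariates with "covs <- subset(smdDataY1, select = c(x1, x2" and an ellipsis. SAP 7.2.1 defines x1 to xn as the time-fixed confounders. SAP 5.8.7 puts the time-fixed covariates in the weighted Cox model because they are in the numerator.

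**The concern.** A balance check should pass good weights and fail bad ones. This one has two faults.

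- For time-fixed covariates (age, sex, SVI, region, payor, year of HIV diagnosis, baseline pneumonia), the weights are built to leave the association with vaccination in place. The SMD after weighting therefore does not measure weight quality. Sections 5.8.4, 5.8.5 and 5.8.7 do not agree on what the weights are meant to balance.
- The smallest interval admitted has 100 vaccinated, where chance error is as large as the limit. The maximum over many such intervals will exceed 0.1 even under perfect balance.

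At stake is the final model. A time-varying covariate flagged by noise may be added to the Cox-MSM. Hospitalization during follow-up is one example: under SAP 5.3.2 it stays recorded once it occurs, and vaccination could reduce it by preventing pneumonia. Conditioning on a covariate that the exposure may affect is what a marginal structural model is meant to avoid. Weights are derived again for each outcome, event type and subgroup, so the choice recurs many times.

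**Working it through.** **Inputs from the documents.** Protocol 9.5: 175,000 people, of whom 56,000 were vaccinated after their first HIV code. Check: 56,000/175,000 = 0.32, as stated. SAP 5.8.5: 30-day intervals, with the last listed day 2910. Check: 2910/30 = 97 intervals, matching 97 months of follow-up. The SAP gives no error rate for the 0.1 rule, so there is no such figure to reproduce. Uptake by interval and crude SMDs are not given either; values for these below are assumptions.

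**Step 1: what the numerator does.** Let A be vaccination in an interval, X a time-fixed covariate and L a time-varying one. With weight P(A|X)/P(A|X,L), the weighted probability of A = a given X is

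Σ_L P(L|X) · P(a|X,L) · P(a|X)/P(a|X,L) = P(a|X).

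The link between A and X is unchanged. L is balanced within levels of X, but it still differs between the groups through X. With numerator P(A) the same sum gives P(a), and both imbalances vanish.

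**Step 2: size for time-fixed covariates.** For a binary covariate with prevalence 0.5 and a vaccination HR of 1.25 (assumed), prevalence among the vaccinated is 0.5 × 1.25/(0.5 × 1.25 + 0.5) = 0.556. The SMD is 0.056/0.499 = 0.11. With prevalence 0.1 and HR 1.5 it is 0.13. At prevalence 0.5 and HR 1.1 it is 0.05, which passes.

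A simulation with true weights (175,000 people, 97 intervals, 12 replicates, flat uptake; time-fixed covariate with prevalence 0.5 and HR 1.5) gave these median absolute SMDs:

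| Covariate | Unweighted | SAP weights | Covariate-free numerator |
|---|---|---|---|
| Time-fixed, predicts vaccination | 0.255 | 0.254 | 0.031 |
| Time-varying, correlated with it | 0.321 | 0.054 | 0.029 |
| Time-fixed, unrelated to vaccination | 0.029 | 0.030 | 0.031 |

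Under the SAP weights the first covariate exceeded 0.1 in 96.5 of 97 intervals on average. The second did so in 14.1, against 4.2 with the covariate-free numerator.

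**Step 3: chance error of one SMD.** With n vaccinated against a much larger unvaccinated group, SE ≈ 1/√n and P(|SMD| > 0.1) = 2[1 − Φ(0.1√n)] under perfect balance.

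- n = 100: SE 0.100, P = 32%
- n = 200: SE 0.071, P = 16%
- n = 577 (56,000/97, even spread): SE 0.042, P = 1.6-1.7%

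Keeping one |SMD| within 0.1 with 95% probability needs (1.96/0.1)² = 384 vaccinated.

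**Step 4: the maximum.** Treating intervals as independent, P(maximum > 0.1) = 1 − Π(1 − P_k) over intervals with at least 100 vaccinated. Even spread: 1 − (1 − 0.0166)^97 = 0.80. If signed values are used (the SAP does not mention absolute values), it is 0.56. Other assumed patterns:

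| Uptake | None vaccinated in baseline | 25% in baseline |
|---|---|---|
| Even | 0.80-0.81 | 0.98 |
| Declining 0.15 per year | 0.94 | 0.995 |
| Declining 0.3 per year | 0.999 | 1.00 |
| Declining 0.6 per year | 0.995 | 0.997 |
| Declining 1.0 per year | 0.97 | 0.96 |

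Keeping the maximum over 97 intervals within 0.1 with 95% probability needs about 1,200 vaccinated per interval; the average available is at most 577. In the simulation, the covariate unrelated to vaccination had a mean maximum of 0.149 under the SAP weights and exceeded 0.1 in 92% of replicates. A covariate-free numerator did not change this (0.151), so each fault needs its own remedy.

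**Step 5: a pooled SMD.** Weighting intervals by number vaccinated gives SE ≈ 1/√56,000 = 0.004, or 1/√33,600 = 0.005 if 40% are vaccinated in baseline. With even uptake the periods 0-3, 3-5 and 5-7 years hold 36, 24 and 25 intervals, so each SE is below 0.01 (for example 1/√(24 × 577) = 0.008).

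**The case against.** A fair defence has several parts.

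- **The time-fixed flag changes nothing in the estimate.** A reader might infer that VE is biased. The documents do not support that: SAP 5.8.7 already adjusts for these covariates in the Cox-MSM, so the only action attached to the flag is already taken. This stands. What remains is an uninformative result and a conflict with the aim in 5.8.4.
- **The SAP does not say that the maximum decides.** The median and maximum are offered as examples, yearly SMDs are shown too, and adding a variable is optional. It would therefore be too strong to say that the rule flags nearly every covariate or forces model changes. This also stands. The median is robust to chance (0.03 for the unrelated covariate), although it can hide imbalance in almost half of the intervals. Leaving the deciding summary open is itself a weakness.
- **It is not the only check.** Weight distributions are summarised and negative controls are planned. The 0.1 rule is the only stated criterion for covariate balance.
- **The probabilities depend on assumptions.** For very rare covariates the normal approximation fails: at an assumed prevalence of 0.1%, with 20-40% vaccinated in baseline, an exact binomial gives 12-86%. In a subgroup of 22,000, even uptake leaves about 0.32 × 22,000/97 = 73 vaccinated per interval and none qualifies, but with declining uptake 6-21 intervals do.
- **The code is an example.** The ellipsis in 7.2.4 does not show that time-varying covariates are left out, since 5.8.5 asks for every covariate.

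**Conclusion.** The concern holds in a limited form. The SMDs of time-fixed covariates cannot serve as a check of these weights. Those that predict vaccination stay above 0.1 (an HR of about 1.25 is enough at prevalence 0.5), weak predictors pass, and correlated time-varying covariates keep part of their marginal imbalance. None of this biases VE.

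If the maximum is held to 0.1, correct weights usually fail: about 0.80 for one balanced, not very rare covariate with even uptake, and about 0.94 or more under assumed declining uptake or 20-40% vaccinated in baseline. These figures treat intervals as independent and ignore weight variability, which would raise them.

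The practical harm is that time-varying covariates possibly affected by vaccination may enter the Cox-MSM because of noise, with no rule on which summary decides. The SAP should be changed before the balance results are used. The yearly SMDs need the same care, because the minimum of 100 vaccinated is stated only for the overall summary.

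**What to change.** For the balance table only:

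1. Compute weights with a covariate-free numerator (vaccination given prior status and interval), or assess balance within levels of the time-fixed covariates. State in 5.8.4 and 5.8.5 that the analysis weights are not meant to balance the time-fixed covariates, which 5.8.7 handles in the model.
2. Apply the 0.1 limit to the absolute value of one SMD per covariate, pooled over intervals with weights equal to the number vaccinated. Also pool by follow-up period (0-3, 3-5, 5-7 years), so that opposite imbalances do not cancel unseen.
3. Show interval-specific and yearly SMDs with their sampling limits and without a pass/fail threshold.
4. Do not add time-varying covariates to the Cox-MSM because of an interval maximum. If the pooled SMD fails, respecify the weight model.
5. Align the example code in 7.2.4, naming both time-fixed and time-varying covariates.

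The cost is SAP wording, a few lines of code and one extra set of diagnostic weights. The analysis weights and the estimand stay as they are.
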